1.5.2 Anticipated Adverse Effects

1.5.2.1 *Potential risks related to using Jabra Enhance Plus as a treatment vs. standard of care*

Compared to the standard-of-care fitting, the only anticipated risks involve the improper self-selection of device settings such that either too little or too much gain will be selected. The maximum possible gain, however, has been limited to minimize the risk to hearing from device use.

1.5.2.2 *Potential risks associated with patient population*

Because the app used to fit and control the device requires some familiarity with such apps, the user may experience some frustration when initially learning how to fit and control the device.

1.5.2.3 *Possible interactions and concomitant treatments*

Because both new and experienced hearing aid users are to be included, experienced user may be frustrated with the differences between the Jabra Enhance Plus device and their own hearing aids, including differences in sound quality and adjustment.

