3.0 OBJECTIVES OF RESEARCH STUDY

3.1 Hypotheses

3.1.1 In-lab validation component-Primary

- Null hypothesis: Mean $|REAG_{PRO-FIT} - REAG_{SELF-FIT}| \geq 2.5$ dB
- Alternative hypothesis: Mean $|REAG_{PRO-FIT} - REAG_{SELF-FIT}| < 2.5$ dB

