3.2 Study Endpoints

3.2.1 Primary Effectiveness Endpoint(s)

For the validation component of the immediate in-lab session comparisons, Real-Ear Aided Gain (REAG) will be measured using both an audiology-best-practices (professional) hearing aid fitting (PRO-FIT) and a self-fitting method (SELF-FIT).

- Success criterion is defined as SELF-FIT REAG is equivalent to PRO-FIT NAL-NL2 prescription REAG targets based on the average real-ear aided gain at 500, 1000, 2000 and 4000 Hz.

For the reliability component of the immediate in-lab session comparisons, Real-Ear Aided Gain (REAG) will be measured twice (A, B) using the SELF-FIT method.

- Success criterion is four-frequency average REAG for SELF-FIT B is equivalent to the REAG for SELF-FIT A based on the average real-ear aided gain at 500, 1000, 2000 and 4000 Hz.

For the wear-time crossover field trial, the APHAB will be measured following both an audiology best-practices hearing aid fitting (PRO-FIT) and a self-fitting method (SELF-FIT).

- Success criterion is defined as SELF-FIT APHAB global score is non-inferior to PRO-FIT APHAB global scores following completion of the wear-time field trial.

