13.1 Management of Data

High data quality standards will be maintained, and processes and procedures utilized to repeatedly ensure that the data are as clean and accurate as possible when presented for analysis. Data quality will be enhanced through a series of programmed data quality checks that automatically detect out of range or anomalous data.

The following practices are adopted to ensure data integrity and participant safety:

1. Data, including outcomes data, should not be shared with GN Hearing A/S until study completion. There are two components to this study: (1) in-lab session (Visit 1); and wear-time crossover trial (Visits 2 and 3). Outcome data can be shared with GN Hearing A/S at the completion of each component to this study. That is, the results from Visit 1 can be shared with the sponsor as soon as they are available and prior to the completion of the entire study.
2. The site investigators should be blinded from the raw data and the research staff on site should enter the data into an electronic database (REDCap). Weekly reports of completed data for each visit will be generated by research staff at each site and will be sent to [name]. Progress reports, generated by [name], will tabulate the number of subjects who have complete data for Visit 1, Visit 2, and Visit 3, for each site separately and combined. Such progress reports will be provided via email to GN Hearing A/S ([name] and [name]) and shared with the site investigators ([name], [name]) on a weekly basis.
3. [name] will monitor the quality of the data exported from REDCap. PRO-FIT REAG values will be checked to determine that they are reasonable, within 5-7 dB of NAL targets, for the measured pure-tone hearing loss for that participant. The pattern across frequency for the REAG differences between test and retest will also be examined to assess data validity. Such differences should generally be less than 5 dB at a given frequency and also should not decrease with increasing frequency. Concerns about the quality of data being gathered will be shared with each site investigator and GN Hearing A/S as soon as possible.

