C. Audioscan Verifit; Speechmap Configuration
(<https://docs.audioscan.com/userguides/vf2manual.pdf>):

[figure not shown]
- i. Targets: Select [NAL-NL2]
- ii. Age: Select [Adult; age \geq 18 years]
- iii. HL Transducer: Select [the Headphone or insert earphone used for testing]
- iv. RECD: Select [average]
- v. Binaural: Select [Yes]
- vi. Language: Select [Non tonal]

D. Audiometric Threshold Entry

- i. On the Threshold entry prompt, enter each threshold from the initial screening using a mouse or an external keyboard. Left click the mouse to enter a point. Click again to delete the point. On the keyboard, the arrow keys change frequency and level and the ENTER key on the numeric keypad enters or deletes a point. The keyboard's numeric keypad can also be used to type in data. Switch sides by moving mouse cursor over to other side.
- ii. Use the X button to erase the curve next to it.
- iii. Use the Copy button at the bottom of the entry screen to copy points on either side to the other side if there are data on one side and no data on the other. The button is disabled and does nothing if both sides contain data or both sides do not contain data.
- iv. Click [check] to save the data and exit the entry screen. In case of error: Click [X] to exit the entry screen without saving the data.

E. Fitting to Targets for Average Speech

Follow the instructions in Speechmap screen choices to enter audiometric data and select the fitting rule (NAL-NL2).

- ii. Click [play] in the "2" area to start the test. Once the test is started, click the [Stimulus] list button to select the stimulus type. Select "Speech-ISTS" as the stimulus type. Click the [Level] list button and select a stimulus level of 65 dB. The upper bar in this area shows the SII for the unaided stimulus at 65 dB SPL.
- iii. PRO-FIT ONLY: While the passage is being presented, adjust the hearing instrument's frequency shaping and gain for average sounds so that the middle curve (the LTASS) falls within the target range, shown by the  symbols.
- iv. Click [record] to signal average and store a complete passage. Repeat as necessary.
- v. In case of error: Click [black square] to stop the test without recording any test data.

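### The in-lab validity criterion names the NAL-NL2 targets, but the planned test compares SELF-FIT only with measured PRO-FIT, so a miss shared by both fits goes untested

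*Combined protocol and SAP*

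**What the plan says.** The in-lab validity endpoint is described with two different references.

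- **Targets.** Section 3.2.1, like the synopsis, states: "Success criterion is defined as SELF-FIT REAG is equivalent to PRO-FIT NAL-NL2 prescription REAG targets based on the average real-ear aided gain". The average is over 500, 1000, 2000 and 4000 Hz.
- **Measured PRO-FIT.** Section 3.1.1 states: "Null hypothesis: Mean $|REAG_{PRO-FIT} - REAG_{SELF-FIT}| \geq 2.5$ dB", with the alternative below 2.5 dB. Section 8.1.2 plans a paired equivalence t-test of the initial SELF-FIT A settings against the initial PRO-FIT settings. Its supplementary analyses (distribution of differences, correlation) also concern those two fits only.

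On how close PRO-FIT must come to target, 6.2.2 and Attachment B tell the audiologist to adjust the device toward the NAL-NL2 targets, in Attachment B "so that the middle curve (the LTASS) falls within the target range". Neither gives a tolerance in dB in its text. The one number is in 13.1 item 3, among the checks on exported data: "PRO-FIT REAG values will be checked to determine that they are reasonable, within 5-7 dB of NAL targets". The stated consequence is that "Concerns about the quality of data being gathered will be shared with each site investigator" and with the sponsor.

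Attachment B also has sites record how close the SELF-FIT response is to target, and save targets and measured responses for both fits.

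**The concern.** If the claim is that SELF-FIT delivers the prescription, a comparison with measured PRO-FIT supports it only as far as PRO-FIT itself sits on the prescription. The two fits share much that could move them in the same direction: the same device (2.2), the same fitting rule (2.1.1.2, 6.2.6), the same earbud size in each ear (6.2.1) and the same gain limit, of which 1.5.2.1 says: "The maximum possible gain, however, has been limited to minimize the risk to hearing from device use". A shortfall common to both would leave their difference near zero. The trial could then meet 3.1.1 without having shown what 3.2.1 describes, and Section 8.1 contains no analysis that would report the distance of either fit from target.

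**Working it through.** **Inputs from the documents.** Margin 2.5 dB (3.1.1); planned sample 36 (5.1); screen 5-7 dB (13.1 item 3); significance level 0.05 (synopsis, equivalence statement). The documents give no SD for REAG differences, so 1 to 5 dB is assumed. The only sample-size figure the plan derives is for APHAB: 32 subjects, SD of differences 0.163, margin 0.084. It reproduces (power 0.805 by noncentral t with 30 degrees of freedom, one-sided 0.025) and has no bearing on this point.

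**Step 1: what the planned test can see.** For one subject, let S and P be the four-frequency average REAG under SELF-FIT A and PRO-FIT, and T the target. Then

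S − P = (S − T) − (P − T).

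T drops out. If both fits are c dB from target, S − P = c − c = 0 whatever c is.

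**Step 2: size of the effect.** Simulation with n = 36, 20,000 runs and alpha 0.05. Sections 3.1.1 and 8.1.2 allow two readings of the test, so both were run: two one-sided tests on the signed mean difference, and an upper confidence bound on the mean absolute difference. Pass rates are shown as signed mean / mean absolute.

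| Assumed SD of S − P (dB) | Both fits on target, or both 5 or both 7 dB below | PRO-FIT 5 below, SELF-FIT 7 below |
|---|---|---|
| 1 | 100% / 100% | 90% / 90% |
| 2 | 100% / 99% | 43% / 17% |
| 2.5 | 100% / 62% | 33% / 4% |
| 3 | 100% / 12-13% | 25% / 0.5% |
| 4 | 96% / about 0% | 18% / about 0% |
| 5 | 80% / 0% | 15% / 0% |

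The middle column is one column because the three cases agree to within simulation error. The pass rate depends on the SD and on the reading of the test, but not on the shared offset.

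**Step 3: the same SELF-FIT judged against target.** Replace P by T. With SELF-FIT 5 or 7 dB from target, the pass rate was 0% under both readings at SDs of 1, 2, 3, 4 and 5 dB. The choice of reference can therefore reverse the result.

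**Step 4: the opposite case.** With PRO-FIT 5 or 7 dB off and SELF-FIT on target, the planned test passed 0% of the time. A poor comparator alone makes the trial fail.

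**Step 5: the scale of the screen.** Suppose, as an assumption, that 5-7 dB applies per frequency and that misses are independent and uniform within ±L.

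- L = 5: per-frequency SD 5/√3 = 2.89; four-frequency average 2.89/2 = 1.44; SE of the 36-subject mean 1.44/6 = 0.24 dB.
- L = 7: 7/√3 = 4.04; 4.04/2 = 2.02; 2.02/6 = 0.34 dB.

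Both standard errors are well inside 2.5 dB. Random misses within the screen would do little to the group mean; only a systematic one matters.

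**The case against.** The strongest reply is that measured PRO-FIT is the intended and legitimate reference. Section 2.2 says the study compares two ways of fitting one device, 8.4 repeats that comparison, and the wording in 3.2.1 may be a loose reference to a PRO-FIT fitted to target. A gain limit, if it bound, would constrain the device however it was fitted. That is a fair defence of 3.1.1, but it leaves 3.2.1 in conflict with it.

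A reader might go further and infer that the plan accepts PRO-FIT as valid at two to almost three times the margin (5/2.5 = 2.0; 7/2.5 = 2.8), so that SELF-FIT is bounded only to within 2.5 + 5 = 7.5 to 2.5 + 7 = 9.5 dB of target. The documents do not support this, for three reasons.

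- The 5-7 dB figure is a plausibility check on exported data. The fitting instructions are to match the targets.
- The two numbers are on different scales. The screen applies to a participant's values with the scale unstated; the companion check on test-retest differences is per frequency ("Such differences should generally be less than 5 dB at a given frequency"). The margin applies to a group mean of four-frequency averages. Their sum is not a bound.
- A false pass needs both fits to miss systematically, in the same direction and by similar amounts. The documents give no value for the gain limit and do not say that it binds at a 65 dB input.

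Nor is it right that a shared miss would leave no trace: Attachment B records SELF-FIT's closeness to target, and the 13.1 check compares PRO-FIT with target. What stands is that neither is a planned analysis in Section 8.1.

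**Conclusion.** The point holds as an inconsistency of reference with a missing analysis. The stated criterion is equivalence to targets, while the planned test is against measured PRO-FIT and cannot detect an offset common to both fits. The cancellation follows from algebra and needs no assumption. The pass rates rest on an assumed SD of 1 to 5 dB and on hypothetical offsets. Whether a shared offset will occur cannot be judged from the documents. The 13.1 screen does not fill the gap, because it has two limits, no scale and no consequence beyond notification. None of this makes the comparison with PRO-FIT wrong in itself; it limits what a pass can be said to show. The correction is worth making before analysis.

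**What to change.** 1. Reconcile 3.2.1 and the synopsis with 3.1.1 and 8.1.2, so that one reference is named throughout for the in-lab validity endpoint.
2. In 8.1.2, add SELF-FIT A minus target and PRO-FIT minus target on the four-frequency average, each with a confidence interval, read against the 2.5 dB margin. The targets and responses saved under Attachment B suffice. Under 6.2.3 the input level is subtracted from both, so REAG minus REAG target equals REAR minus REAR target.
3. In 13.1 item 3, replace the range by a single figure and say whether it applies per frequency or to the four-frequency average.

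I would not add a 2.5 dB fitting limit per ear, which turns a group-mean margin into an individual tolerance without a basis in the documents. Nor would I repeat the primary test only in subjects whose PRO-FIT came close to target: that selects on a result obtained after fitting and shrinks a sample of 36.

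The cost is one extra table, with no new measurement, visit or subject. The downside for the sponsor is that the table may show a less favourable distance from target than the comparison between fits does.

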13.2 Subject De-Identification

At the end of the study, all study databases will be de-identified and archived at the designated data coordinating center.

Data collected for this study will be analyzed and stored at the data coordinating center. After the study is completed, the de-identified, archived data will be transmitted to and stored at the designated data repository, for use by other researchers including those outside of the study. Permission to transmit data to the data repository will be included in the informed consent.

When the study is completed, access to study data and/or samples will be provided through the data repository.

13.3 Site Record Retention

Site Record retention will be defined by the IRB policies at Vanderbilt University, Northwestern University, and Sertoma Speech and Hearing Center.

14.0 MONITORING PLAN

14.1 Brief Description

In collaboration with investigational site(s), the Sponsor will ensure proper monitoring of the study to confirm that all Sponsor obligations are met and that the study is performed in accordance with the CIP. Monitoring calls and emails will ensure adherence to the CIP, completion of informed consents, IRB/IEC review of the study, maintenance of records, primary outcomes review and source documentation for accuracy and completeness. Further information and details regarding monitoring arrangements can be found in the monitoring plan.

14.2 Reference to Approved Monitoring Plan

The approved monitoring plan will be maintained by the Sponsor or its delegate throughout the study.

15.0 PUBLICATION POLICY

Any publication of the results from this study must be consistent with the Sponsor's publication policy. The rights of the investigator and of the Sponsor with regards to publication of the results of this study/registry are described in the investigator contract.

The results of this study are intended for use in submission to the FDA in support of a 510k submission for the Jabra Enhance Plus device. This study will be registered into the clinicaltrials.gov website.

16.0 ADDITIONAL STUDY MATERIALS

ATTACHMENT A: See attached clinical study user's manual for Jabra Enhance Plus

ATTACHMENT B: Real-ear measurement details

A. **SELF-FIT A & B:** Personalization begins with an estimate of hearing acuity obtained through the Jabra Enhance Plus. The hearing acuity measurements are used internally by the device and are not shared with the hearing aid wearer. Once this step has been completed, devices will apply NAL-NL2 gain prescriptions directly using the estimated hearing acuity to generate the initial fit. For the clinical validation study, probe-tube microphone measures of the REUR and REAR (REAG=REAR in input) will be obtained on the initial fit for a 65-dB speech input using the Audioscan Verifit real-ear measurement system, with instructions as follows:

[figure not shown]
- i. Use the Audioscan Verifit (see procedure below) to measure Real Ear Aided Response (REAR) using the GN-supplied dome/probe tube assembly.
- ii. Without adjusting the gain, determine how close the 65 dB-Input referenced Response curve from the output of the device is to the NAL-NL2 65 dB REAR Targets in the Verifit 1 or 2.
- iii. Audioscan includes a method for saving measurements to a USB drive. Please use this method for saving the REAR measurements and Targets for analysis of the output.
- iv. The file saved to the USB drive should include a .html or .csv file with frequency-specific values that can be used for plotting and analyzing the results.

B. **PRO-FIT:** Audiometric thresholds will be imported, and the devices programmed using custom device programming software (AlgoLabTest) and configured for NAL-NL2 target gains. Probe-tube microphone measures of the REUR and REAR (REAG=REAR-REUR) will be obtained for a 65-dB speech input using the Audioscan Verifit real-ear measurement system, with instructions as follows:

- i. Use the Audioscan Verifit (see procedure below) to measure Real Ear Aided Response (REAR) using the GN-supplied dome/probe tube assembly.
- ii. Using AlgoLabTest to adjust the gain, attempt to match the 65 dB Gain curve from the output of the device to the NAL-NL2 65 dB Gain Targets in Verifit.
- iii. Audioscan includes a method for saving measurements to a USB drive. Please use this method for saving the REAR measurements and targets for analysis of the output.
- iv. The file saved to the USB drive should include a .html or .csv file with frequency-specific values that can be used for plotting and analyzing the results.

C. Audioscan Verifit; Speechmap Configuration
(<https://docs.audioscan.com/userguides/vf2manual.pdf>):

[figure not shown]
- i. Targets: Select [NAL-NL2]
- ii. Age: Select [Adult; age \geq 18 years]
- iii. HL Transducer: Select [the Headphone or insert earphone used for testing]
- iv. RECD: Select [average]
- v. Binaural: Select [Yes]
- vi. Language: Select [Non tonal]

D. Audiometric Threshold Entry

- i. On the Threshold entry prompt, enter each threshold from the initial screening using a mouse or an external keyboard. Left click the mouse to enter a point. Click again to delete the point. On the keyboard, the arrow keys change frequency and level and the ENTER key on the numeric keypad enters or deletes a point. The keyboard's numeric keypad can also be used to type in data. Switch sides by moving mouse cursor over to other side.
- ii. Use the X button to erase the curve next to it.
- iii. Use the Copy button at the bottom of the entry screen to copy points on either side to the other side if there are data on one side and no data on the other. The button is disabled and does nothing if both sides contain data or both sides do not contain data.
- iv. Click [check] to save the data and exit the entry screen. In case of error: Click [X] to exit the entry screen without saving the data.

E. Fitting to Targets for Average Speech

Follow the instructions in Speechmap screen choices to enter audiometric data and select the fitting rule (NAL-NL2).

- ii. Click [play] in the "2" area to start the test. Once the test is started, click the [Stimulus] list button to select the stimulus type. Select "Speech-ISTS" as the stimulus type. Click the [Level] list button and select a stimulus level of 65 dB. The upper bar in this area shows the SII for the unaided stimulus at 65 dB SPL.
- iii. PRO-FIT ONLY: While the passage is being presented, adjust the hearing instrument's frequency shaping and gain for average sounds so that the middle curve (the LTASS) falls within the target range, shown by the  symbols.
- iv. Click [record] to signal average and store a complete passage. Repeat as necessary.
- v. In case of error: Click [black square] to stop the test without recording any test data.
- vi. Upon completion of a test recording, a colored Aided Audibar shows the SII for the aided average speech signal. The difference between the unaided and aided SII score (and the associated length of their respective 'Audibars') visually quantifies the speech intelligibility improvement for soft speech likely provided by the hearing instrument being fit.

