Primary Safety Objectives/Endpoints:	
Tabulations of Adverse Events (AEs) and Serious Adverse Events (SAEs).
 
○ Success criterion is no recorded device-related AEs or SAEs.
Inclusion Criteria:	
An initial telephone or internet screening of interested persons will take place.
 
• During this remote screening, prospective subjects will provide their age (subject to verification at Visit 1) and answer a Yes/No question as to whether they have trouble hearing in noise. Those answering "No" will not be considered further for enrollment.• Those answering "Yes" will then be asked to describe their perceived hearing loss on a 4-point scale (no trouble, a little trouble, a lot of trouble, and cannot hear). Prospects answering at the two extremes will not be considered further for this study.• Those answering "a little trouble" or "a lot of trouble" will be invited to the in-person Screen that immediately precedes hearing aid fittings in Visit 1. To be eligible to participate in this study, an individual must meet all of the following criteria:

	
 • Mild-to-moderate bilateral sensorineural hearing loss (thresholds from 250 – 8000 Hz with at least one threshold greater than 20 dB HL and thresholds at 500, 1000, 2000 and 4000 Hz less than or equal to 55, 65, 70, and 80 dB HL, respectively) • Mix of male and female subjects (aiming for a representative balance) • Mix of prior hearing-aid use (aiming for 70-80% persons with no prior hearing aid use) • 18-75 years old (aiming for primarily 50-70 years old, with avg. age ~65 years) • Able to read and comprehend English • Patient willing to provide informed consent
Exclusion Criteria:	
An individual who meets any of the following criteria will be excluded from participation in this study:
 
 • Hearing outside of limits noted above • Self-reported ear-related pathology (including chronic severe dizziness or chronic severe tinnitus)
Sampling Frame:	
The proposed sample size of n=36 subjects will be sufficient to rule out a null hypothesis of non-equivalence of SELF-FITs A and B (reliability) or SELF-FIT A and PRO-FIT (validity) with about 80% power with 0.05 significance level. In addition, distributions of deviations from the standard-of-care measures will be generated for the primary and secondary measure and for the reliability and validity components of the study.

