3.1.5 In-Lab Session-Reliability Component-Primary

- Null hypothesis: Mean $|REAG_{SELF-FIT A} - REAG_{SELF-FIT B}| \geq 2.5$ dB
- Alternative hypothesis: Mean $|REAG_{SELF-FIT A} - REAG_{SELF-FIT B}| < 2.5$ dB

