5.0 STUDY SUBJECTS

5.1 Sample Size Determination

The sample size was powered by the primary outcome measure of the wear-time field trial, the APHAB, as it is the most variable of the outcome measures across all components of this study. When the sample size in each sequence group in the crossover trial is 16 (giving a total sample size of 32), a crossover design will have 80% power to reject the null hypothesis that the SELF-FIT APHAB mean is inferior to the PRO-FIT APHAB mean based on the mean difference, in favor of the alternative hypothesis that the SELF-FIT mean is non-inferior to the PRO-FIT mean, assuming that the expected difference in means is 0, the non-inferiority difference margin is .084 (or 8.4%), the Crossover ANOVA \sqrt{MSE} is 0.115 (or 11.5%) (giving a standard deviation of differences, σ , of 0.163 or 16.3%) and that the test is made at the 2.5% significance level.

The overall design for the in-lab session is a repeated-measures design comparing outcomes for three procedures: SELF-FIT A, SELF-FIT B, PRO-FIT. Given that SELF-FIT A and B are the same procedure repeated two times, this results in three possible procedure sequences: (1) SELF-FIT A, SELF-FIT B, PRO-FIT; (2) SELF-FIT A, PRO-FIT, SELF-FIT B; and (3) PRO-FIT, SELF-FIT A, SELF-FIT B. An equal number of subjects will receive each sequence at each site to ensure full counterbalancing of order. A total of 36 subjects, 18 per site, will be included which meets the minimum of 32 required for sufficient statistical power, achieves the desired counterbalancing, and allows for some subject attrition or missing data.

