6.2.6 REAR Measurement and REAG Calculation

SELF-FIT A & B: Personalization begins with an estimate of hearing acuity obtained through the Jabra Enhance Plus. The hearing acuity measurements are used internally by the device and are not shared with the wearer. Once this step has been completed, devices will apply NAL-NL2 gain prescriptions directly using the estimated hearing acuity to generate the initial fit. Probe-tube microphone measures of the REAR (REAG=REAR-input) will be obtained for a 65-dB speech input using the Audioscan Verifit real-ear measurement system. All probe-tube microphone measures will make use of the custom dome/probe-tube assembly supplied by GN Hearing. (Attachment B for details.)

PRO-FIT: Audiometric thresholds will be imported and the devices programmed using custom device programming software (AlgoLabTest) for NAL-NL2 target gains. Probe-tube microphone measures of the REUR and REAR (REAG=REAR-input) will be obtained for a 65-dB speech input using the Audioscan Verifit real-ear measurement system. All probe-tube microphone measures will make use of the custom dome/probe-tube assembly supplied by GN Hearing. (See Attachment B for details.)

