8.1.2 In-Lab *REAG – Validity* (initial Pro-Fit vs initial Self-Fit A)

- i. Paired-sample t-test for equivalence of the means of the initial-fit settings of the SELF-FIT A procedure to the means of the initial-fit settings of the PRO-FIT procedure
- ii. Supplementary analyses will include examination of the distribution of differences in dB between the four-frequency average REAGs for initial-fit settings of the SELF-FIT A procedure and initial-fit settings of the PRO-FIT procedure, as well as computation of correlation coefficients between the two measures.

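### Attachment B sets no rule on when a primary REAG recording may be repeated or which recording is analysed, although the operator knows the fit and sees the target

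*Combined protocol and SAP*

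**What the plan says.** Section 3.1.1 states the in-lab validity alternative as "Mean $|REAG_{PRO-FIT} - REAG_{SELF-FIT}| < 2.5$ dB" and section 3.1.5 states the reliability alternative as "Mean $|REAG_{SELF-FIT A} - REAG_{SELF-FIT B}| < 2.5$ dB". Sections 1.5.3.1 and 8.4 require every primary endpoint to be met for the study to succeed, so each REAG endpoint can fail it alone.

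Section 6.2.6 gives the measurement: "Probe-tube microphone measures of the REAR (REAG=REAR-input) will be obtained for a 65-dB speech input". Attachment B gives the operating steps:

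- Parts C to E: the operator enters the thresholds and selects NAL-NL2 targets on the Verifit.
- Part A, item ii (SELF-FIT): with gain left alone, the operator is to "determine how close the 65 dB-Input referenced Response curve from the output of the device is to the NAL-NL2 65 dB REAR Targets". Item iii then asks for measurements and targets to be saved to USB.
- Part E, item iii: gain adjustment during the passage, marked as applying to PRO-FIT alone.
- Part E, item iv: "Click [record] to signal average and store a complete passage. Repeat as necessary". This item carries no such restriction.
- Part E, item v: a separate step for stopping a run in error without storing data.

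The single-blind label in section 4.1 belongs to the field trial. Section 13.1 keeps site investigators from the raw data but does not cover the person recording. Section 4.2 lists bias controls, and none masks the REAG measurement.

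**The concern.** One step in the sequence applies to PRO-FIT alone, so the operator has to know which fit is being measured, although the protocol never says so outright. The operator is also asked to compare the SELF-FIT curve with the displayed target. The next action is a recording that may be repeated at discretion. PRO-FIT is meant to be iterated to target, whereas SELF-FIT is meant to be measured as it comes. The repeat instruction does not make that distinction.

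If curves that look far from target were repeated more often than curves that look close, and the closer one kept, the SELF-FIT to PRO-FIT difference would shrink. So would the A to B difference. The bias runs one way, towards declaring equivalence and reliability. The section 13.1 quality checks compare PRO-FIT with target (within 5-7 dB) and look for large test-retest differences (5 dB or more at a frequency). Neither would reveal a superseded SELF-FIT recording.

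**Working it through.** **The plan's own figure.** The only sample-size calculation (section 5.1) is for APHAB: √2 × 0.115 = 0.163. With margin 0.084, one-sided 2.5% and noncentral t on N − 2 degrees of freedom, power is 0.805 at N = 32, which matches the stated 80%. No REAG variance or REAG calculation is given. The present point does not touch N = 32.

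**Inputs from the documents.** Limit 2.5 dB on the mean absolute difference; 36 subjects. The significance level is stated in two ways: the synopsis has "with about 80% power with 0.05 significance level" for the in-lab comparisons, and section 5.1 has "that the test is made at the 2.5% significance level" for APHAB. Both levels are shown below.

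**Assumed.** Recording-to-recording SD *s* of the four-frequency average (0.5, 1.0, 1.5 dB), normal differences centred on zero, and the operator's repeat behaviour. None of these is in the documents.

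**Set-up at the limit.** For a centred normal difference, mean |d| = σ√(2/π). Setting this to 2.5 gives σ = 2.5/0.798 = 3.13 dB. The part not due to recording noise has SD √(3.13² − s²): 3.09, 2.97 and 2.75 dB. The share of subjects with |d| above 2.5 dB is 2 × [1 − Φ(2.5/3.13)] = 42%. The test is t = (mean|d| − 2.5)/(SD/√36), passing when t is below the lower 5% point on 35 degrees of freedom.

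**Simulated false-pass rate, nominal one-sided 5%, at most one repeat per subject:**

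| Behaviour | s = 0.5 | s = 1.0 | s = 1.5 |
|---|---|---|---|
| No repeats | 7% | 7% | 7% |
| A quarter of curves beyond 2.5 dB repeated, closer kept | 9% | 11% | 15% |
| All beyond 2.5 dB repeated, repeat kept whether closer or not | 9% | 18% | 36% |
| All beyond 2.5 dB repeated, closer kept | 16% | 36% | 65% |

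The baseline is 7% rather than 5% because absolute differences are skewed. In the last row the mean absolute difference falls from 2.50 to 2.36, 2.17 and 1.97 dB. At a nominal 2.5% the last row is 10%, 27% and 54%, against a baseline of 4%.

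**If the test is on signed means.** Section 8.1.2 specifies "Paired-sample t-test for equivalence of the means of the initial-fit settings of the SELF-FIT A procedure", which could be read as two one-sided tests on signed differences. With a true signed mean of 2.5 dB, an assumed between-subject SD of 2 dB and the recording nearest target kept out of three, the false-pass rate rises from 5% to 28%, 65% and 96% at s = 0.5, 1 and 2 dB. The direction does not depend on the form of the test.

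**Reliability.** Keeping the recording nearest target out of three for both A and B (assumed shared subject offset SD 2 dB) lowers mean |A − B| from 2.50 to 2.18, 1.86 and 1.37 dB at s = 0.5, 1 and 2 dB.

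**Limit of the effect.** A SELF-FIT curve truly 5 dB off target still averages 4.58, 4.15 and 3.33 dB off after best of three at s = 0.5, 1 and 2 dB. Even best of ten leaves 4.23, 3.46 and 2.00 dB.

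**The case against.** A reader might infer that an off-target SELF-FIT curve can be re-recorded until it looks right, or that operators will do this. The documents support neither. SELF-FIT gain may not be changed, so repeats draw only on recording and placement variability, and the 5 dB example shows how little a few repeats achieve. No step tells the operator to repeat for closeness to target, to re-seat the probe or earbud, or to compare B with A. The repeat instruction sits among generic instrument steps and reads naturally as covering a poor recording.

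The display also has a purpose. Section 3.2.1 words validity success in terms of NAL-NL2 targets, and the targets must be saved with the measurements. The closeness step may therefore mean later analysis rather than acceptance at the screen. In two of the three sequences in section 5.1, SELF-FIT A comes before PRO-FIT, so the endpoint difference cannot yet be seen and target is only a proxy. The operator sees a curve across frequency, not the four-frequency average. The highest rates in the table need a result exactly on the limit, every far curve repeated, and the closer value always kept.

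All of this stands, and it limits the size of the concern. It does not close the gap. Item v already deals with a run stopped in error, so repeats of completed recordings under item iv are left to judgement. Nothing says which recording counts or requires the others to be kept. Whether the saved file would show a repeat cannot be determined, because its content is described only as frequency-specific values.

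**Conclusion.** The point holds as a gap in the measurement rule for two primary endpoints. The text permits selective repetition. It does not instruct it, and nothing shows that it would occur. Any selection towards target would favour passing, and it matters when the result lies near 2.5 dB rather than when SELF-FIT is clearly off.

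The size is not known from the documents. With the mean absolute difference on the limit and an assumed recording SD of 0.5 to 1.5 dB, the false-pass rate goes from about 7% to about 9-15% if a quarter of far curves are repeated. It goes to about 16-65% if all are repeated. In both cases the closer value is kept. The lower range is the milder reading and the upper range is close to a worst case. This is a cheap improvement worth making, not a flaw that invalidates the design.

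**What to change.** In Attachment B, part E, item iv, for SELF-FIT A, SELF-FIT B and the verification recording of the locked PRO-FIT initial fit:

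- Store one complete passage.
- Repeat only for a technical fault (noise intrusion, probe blockage, interrupted passage), logged with its reason.
- Analyse the first technically valid recording.
- Keep every recording, including superseded ones, on the USB export.

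In part A, item ii, state that closeness to target is calculated from the saved file and is not a reason to repeat. Iteration while PRO-FIT is being adjusted to target stays as it is.

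The operator would still know the fit and see the target; the change works by removing discretion over which recording counts. It costs wording and one log line. The export is already required, and no visit, staffing, device setting or sample size changes. The downside is slightly noisier single recordings.
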